1 CLINICAL PROTOCOL SYNOPSIS

Sponsor	Aerogen Pharma
Protocol Number	APC-AF-CLN-002
Title of Study	A Partially-Blind, Randomized, Controlled, Parallel-Group Dose Ranging Study to Determine the Efficacy, Safety and Tolerability of AeroFact™ (SF-RI 1 surfactant for inhalation combined with a dedicated drug delivery system) in Preterm Infants at Risk of Worsening Respiratory Distress Syndrome
Study Centers	Multicenter
Phase of Development	Phase 2b
Objectives	
Part I
 
Primary Objective
 
To determine an optimal dose of AeroFact™ administered to preterm infants on nCPAP or nIMV vs. nCPAP or nIMV alone in reducing the incidence of intubation/cannulation and bolus surfactant instillation in the first 7 days after birth.
 
Secondary Objectives
 
 • To compare the time to the first intubation/cannulation across groups for infants requiring intubation due to surfactant deficiency • To compare need for repeat surfactant dosing between groups within 7 days • To evaluate the safety and tolerability of AeroFact administered by inhalation 
Part II
 
Additional Objectives
 
 • To evaluate pulmonary outcomes and respiratory resource utilization at 3, 6, 9, and 12 months corrected age • To evaluate respiratory morbidity per quarter and compare pulmonary morbidity across groups • To evaluate early neurologic Gross Motor Function Score (modified GMFS) outcomes at 12 months corrected age
Study Design	
This partially-blind, randomized, controlled, parallel-group, dose-ranging study is divided into 2 Parts. Part I includes birth through 40 weeks PMA or hospital discharge (treatment) and Part II discharge through 12 months corrected age (Follow Up).
 
Part I
 
Part I is to determine the optimal dose of AeroFact administered to preterm infants on nCPAP or nIMV (Active) vs. nCPAP or nIMV alone (Control) in reducing the incidence of intubation/cannulation and bolus surfactant instillation in the first 7 days after birth. 261 preterm infants who are at risk of worsening Respiratory Distress Syndrome (RDS) will be enrolled. The AeroFact dose and dosing strategy determined in this study will be used in

	
a Phase 3 definitive trial. Preterm infants who require nCPAP (either by bubble CPAP or machine CPAP) or nIMV, and meet the inclusion and no exclusion criteria, will be enrolled into the study.
 
In the delivery room, infants will be stabilized on nCPAP/nIMV per site clinical guidelines. Once the infant has been stabilized, determined as eligible, and parental consent obtained, the infant will be block randomized in a 1:1:1 partially-blind fashion to receive one of two doses of AeroFact or Control. The randomization will be stratified by site and two gestational age groups (26 0/7 to 28 6/7 and 29 0/7 to 31 6/7 weeks). Patients who meet all inclusion and no exclusion criteria and are randomized to receive an Active dose, will have the initial assigned treatment administered within the first twenty-four hours after birth. Patients who are assigned to the Control group will continue to receive nCPAP/nIMV. If twins or triplets are enrolled, only the first sibling will be randomized and subsequent siblings will receive the same treatment assignment.
 
Active treatment dose allocation will be unblinded to pharmacy and respiratory dosing staff or designees. All other hospital personnel will be blinded. Randomization will be a two-step process. Step 1: a designated member of the study staff will obtain a randomization envelope for the appropriate gestational age group, which will randomize the infant to either the Active or Control group. Step 2: active envelopes will be forwarded to the unblinded pharmacist or designee, where the active envelope will be opened and allocation to the Low or High dose group (108 mg/kg or 216 mg/kg) will be determined. Active drug dose will be calculated and dispensed according to the pharmacy manual instructions. Active drug will be administered according to study protocol.
 
For AeroFact dosing, oxygenation, ventilation parameters, and nasal congestion/aspiration will be monitored every 15 minutes for duration of dosing or a minimum of two hours by a blinded study/staff member. Dosing tolerance will be evaluated at 4 and 24 hours after the start of each AeroFact dose. Oxygenation, ventilation parameters, nasal congestion/aspiration and dosing tolerance will also be collected after each bolus surfactant instillation at similar timepoints. AeroFact tubing/nebulizer and vial will remain in place for a minimum of 2 hours. The AeroFact delivery system will be removed from the patient's bedside after dosing has been completed or a minimum of 2 hours. The patient may be transitioned back to their standard nCPAP interface. A new AeroFact drug delivery circuit must be used for each dose administered.
 
Infants receiving active drug will continue on nCPAP/nIMV after dose completion. If oxygenation and ventilation requirements increase within 96 hours of birth, AeroFact administration may be repeated up to three times for a total of 4 doses over the first 96 hours after birth. Re-dosing of AeroFact (same randomized group) will be allowed if the RSS is 1.5 to 2.39 and at least two hours have elapsed since the start of the previous dose:
 
• If $\text{FiO}_2 > 0.23$, re-dosing will occur.• If $\text{FiO}_2 \leq 0.23$, re-dosing is at the discretion of the investigator. 
SpO₂ between 90-95% must be used to meet study eligibility through 96 hours for all study groups (Active/Control). Site-specific SpO₂ clinical guidelines may be used after 96 hours. Each site must use these guidelines uniformly across treatment groups. Infants randomized to the Control group will be clinically managed until the criteria for treatment escalation have been met. If at any time the criteria for treatment escalation are met in any of the three treatment arms, intubation and/or bolus instillation of surfactant may be administered at the discretion of the clinical team.
 
Criteria for treatment escalation for AeroFact or Control groups include any of the

--	--

	
following:
 
 • Respiratory Severity Score (RSS) ≥ 2.4 • Partial Pressure of Carbon Dioxide (PCO_2) $> 65 \text{ mg Hg}$ and/or $\text{pH} < 7.20$ • Base deficit $> 10 \text{ mEq/L}$, on two blood gases 4 hours apart • nCPAP $> 8 \text{ cm}$ • Three severe apneas with bradycardia within six hours requiring escalation of support • Infant's work of breathing has increased warranting escalating therapy, but infant does not meet RSS or other criteria above. 
Study treatment will be discontinued if any of the following occur:
 
 1. Pneumothorax (requiring chest tube) 2. Pulmonary hemorrhage (frank bleeding from the lungs that is not related to irritation due to suctioning or infection) 3. Infant shows evidence of pulmonary hypertension requiring iNO 
Each infant will be clinically assessed and evaluated per protocol during their stay in the NICU, to 40 weeks PMA or discharge, whichever comes first.

	
Part II
 
Patients who survive to 40 weeks PMA or discharge will be eligible for Part II. Part II will begin at discharge/40 weeks PMA and include telephone Questionnaires performed at 3, 6, 9 and 12 months corrected age . Evaluation of home environment, respiratory support, medical history, modified GMFS and respiratory resource utilization after discharge will be collected. (See Appendices for Questionnaires)

Number/Type of Subjects	Approximately 261 (87 per study arm) subjects will be block randomized in a 1:1:1 allocation. This number will be reassessed at the interim analysis.
Inclusion Criteria	
Preterm infants are eligible for this study if they meet all of the following criteria:
 
 1. Parental consent obtained prior to study procedures being performed (pre-natal consent is allowed) 2. 26 0/7 to 31 6/7 weeks of gestational age 3. Weight $< 2000 \text{ grams}$ 4. Weight appropriate for gestational age (AGA 3% to 97%) 5. Age \leq twenty-four hours at the initiation of study treatment 6. RSS ($\text{MAP} \times \text{FiO}_2$) $1.4 - 2.0$ on nCPAP or nIMV 7. Chest radiograph or lung ultrasound [13,14] consistent with a diagnosis of RDS
Exclusion Criteria	
Preterm infants are NOT eligible for this study if they meet any of the following criteria:
 
 1. Apgar score ≤ 5 at five minutes after birth 2. Need for chest compressions or administration of epinephrine or bicarbonate in the delivery room 3. Premature rupture of membranes (PROM) > 14 days, 4. Criterion Removed 5. Base deficit $> 10 \text{ mEq/L}$ on clinically indicated blood gas at time of randomization

	
 6. Need for intubation and/or mechanical ventilation prior to enrollment 7. HFNC and RAM Cannula or are not allowed to determine eligibility 8. Prior instillation of surfactant 9. Enrollment in another treatment study with competing outcomes 10. Active pneumothorax requiring chest tube 11. Significant congenital anomaly 12. Known or suspected chromosomal abnormality 13. Other etiologies of respiratory distress (e.g. meconium aspiration syndrome, hydrops fetalis, toxoplasmosis, rubella, cytomegalovirus, herpes simplex) 14. Concomitant treatment with inhaled nitric oxide 15. Suspected PPHN with sustained pre/post SpO₂ ductal differences > 10%
Study Treatment(s)	
Infants will be block randomized in a 1:1:1 fashion to Active or Control. Stratification across all groups will be by site and gestational age (26 0/7 to 28 6/7 and 29 0/7 to 31 6/7 weeks). Patients randomized to Active drug will receive 1 of 2 nominal dose levels of AeroFact (108 mg/kg or 216 mg/kg).
 
Up to three additional doses of AeroFact within 96 hours of birth will be allowed if RSS is 1.5 to 2.39 and at least two hours have elapsed since the start of the previous dose:
 
 • If FiO₂ > 0.23, re-dosing will occur. • If FiO₂ ≤ 0.23, re-dosing is at the discretion of the investigator. 
SpO₂ between 90-95% must be used to meet study eligibility through 96 hours for all study groups (Active/Control). Site-specific SpO₂ clinical guidelines may be used after 96 hours. Each site must use these guidelines uniformly across treatment groups.
 
All infants randomized will be clinically managed until the criteria for treatment escalation have been met.

Concomitant Therapy	
The use of Vitamin A or corticosteroids for BPD prophylaxis must be consistent, and appropriate for age, for all enrolled infants within each study site.
 
The routine use of corticosteroids for blood pressure (BP) or adrenal support should be avoided during the first 96 hours after birth.
 
HFNC and RAM Cannula are not permitted in the first 96 hours of life.

Duration of Treatment	
The duration of study participation for each infant is as follows:
 
Part I:
 
 • Treatment Period: 96 hours • Study Period: Through 40 weeks PMA or Discharge from NICU (whichever comes first) 
Part II:
 
 • Follow-Up Period: 12 months corrected age
Criteria for Evaluation	
Efficacy Assessments
 
Part I:
 
Primary Efficacy Endpoint
 
 • Proportion of infants requiring intubation/cannulation and bolus surfactant instillation in the first 7 days of life.

	
Secondary Efficacy Endpoints
 
 • Time to first intubation/cannulation and bolus surfactant instillation between study treatments for first 7 days of life • Compare the proportion of infants across groups receiving multiple doses of surfactant. • Number of days on mechanical ventilation from the day of birth to 40 weeks PMA or discharge. • Number of days on supplemental oxygen administration from the day of birth to 40 weeks PMA or discharge • Survival without bronchopulmonary dysplasia (BPD) at 36 and 40 week PMA. (If an infant is discharged from the NICU prior to 36 and/or 40 weeks, a study member will call the family to verify the respiratory support status.) 
Safety and Tolerability Assessments
 
Safety and tolerability will be assessed through the monitoring of oxygenation, bradycardia, nasal congestion/aspiration, and other adverse events of interest (AEs) to 40 weeks PMA or discharge. Incidence of comorbidities of prematurity/AE's will be assessed. Tolerance of the AeroFact dosing administration and all doses of bolus surfactant will be assessed during and up to 24 hours following dosing.
 
Part II:
 
Additional Efficacy Endpoints
 
 • Assessment of pulmonary outcomes at 3, 6, 9 and 12 months corrected age • Length of NICU Stay (LOS) • Proportion of subjects with any respiratory resource utilization at 3, 6, 9 and 12 months corrected age • Respiratory morbidity per quarter till 12 months of corrected age • Assessment of modified GMFS (early neurologic) at 12 months of corrected age
Criteria for Individual Patient Discontinuation	
Aerogen Pharma, the Investigator or parent (s) may discontinue pre-term infants from the study at any time for the following reasons:
 
 • Safety • Withdrawal of parental consent • At the discretion of the Investigator
Statistical Considerations	
Randomization, Stratification and Sample Size:
 
Two hundred and sixty-one (261) subjects (87 in each arm) will be randomized in a 1:1:1 ratio in order to assure that 246 subjects (82 in each arm) complete the study. The randomization will be stratified by site and gestational age.
 
Infants requiring treatment escalation in the AeroFact dose groups is estimated to be 20% and in the control group is estimated to be 40%, with an odds ratio of 0.375.
 
Under the above assumptions, 82 subjects in each treatment group will be required, to meet the Type I error rate of 0.05 and 80% statistical power. To accommodate the potential dropouts, a 5% dropout rate is included in this sample size calculation.
 
Analyses Populations:

	
Intent-to-Treat (ITT) population: The Intent-to-Treat (ITT) population is defined as all randomized subjects. The ITT population will be the primary population for the primary, secondary and additional efficacy analysis.
 
Per Protocol (PP) population: The Per Protocol (PP) population is defined as all randomized subjects who were not associated with a major protocol violation. The PP analysis of primary, secondary and additional endpoints will be considered supportive.
 
Safety population: The Safety population is defined as all randomized subjects . This population will be used for the analysis of safety parameters.

Interim Analysis	
A blinded interim analysis is planned and will be conducted when approximately 60% of subjects have been randomized and completed first 7 days of life or early terminated, whichever occurs first.
 
The main purpose of this interim analysis will be:
 
 sample size re-assessment to evaluate the final sample size needed to proceed with the study based on the control responder rate at interim analysis, and;to evaluate the safety of AeroFact on the frequency of adverse events, nasal congestion/aspiration, dosing tolerance events, and serious adverse events
Efficacy Analyses	
The primary analyses of the primary, secondary, and additional efficacy endpoints will be conducted on the ITT population. The PP population analyses of primary, secondary, and additional endpoints will be considered supportive.
 
For the efficacy endpoints the data will be summarized and compared according to the variable type:
 
 Continuous data summaries will include: 
 Descriptive summary of number of observations, mean, standard deviation, median, and minimum and maximum values. Analysis of Covariance (ANCOVA) or Mixed Model Repeated Measures (MMRM) adjusted for stratification factors for inferential statistics. Categorical data summaries will include: 
 Frequency counts and percentages Logit model or Generalized Estimating Equation (GEE) method adjusted for stratification factors and clustering of multiple births within a mother for inferential statistics Time-dependent data: Cox proportional hazards model will be used to analyze time dependent data and to depict the time to event data.
Safety Analyses	
Safety will be evaluated on the Safety Population.
 
The number and percent of infants experiencing TEAEs, serious adverse events, and TEAEs leading to study discontinuation will be summarized for each treatment group by Medical Dictionary for Regulatory Affairs (MedDRA) system organ class and/or preferred term. Additional summaries will include TEAE severity and relationship to study drug.

PK Sampling	Not applicable

Table 1 – Schedule of Assessments and Procedures – Part I and Part II

Part I								Part II
		Day 1	Day 2-4	Day 5 – Day 28	36 Weeks PMA	40 Wks PMA	Discharge	3, 6, 9, 12 Months Corrected Age
Informed Consent ¹	X							
Demographics		X						
Maternal/Infant Medical History		X						
Chest Radiograph or Lung Ultrasound		X						
Medication History		X						
Inclusion/Exclusion Criteria		X						
Randomization		X						
Clinical Blood Gas Assessments ²		X	X					
Weight, Recumbent Length, Head Circumference ³		X					X	X
Administer AeroFact or begin nCPAP/nIMV alone ⁴⁻⁵		X	X					
Oxygenation and Respiratory Parameters ⁶⁻⁷		X	X	X	X ⁸	X ⁸		
Nasal Congestion Assessment ⁹		X	X					
Dosing Tolerance ¹⁰		X	X					
AE/Co-Morbidities Monitoring		X	X	X	X		X	
Concomitant Medications		X	X	X	X		X	
Feeding Status/Pulmonary Questionnaire/Audiology/Ophthalmology Reports							X	
Room Air Challenge (RAC) ¹¹					X	X		
Follow-Up Telephone Questionnaire ¹²								X

¹ Informed consent may be obtained prenatally² Blood gases (pH, PCO₂, PO₂, HCO₃-, base deficit) will be obtained prior to enrollment and intubation or in relationship to an SAE (if clinically obtained).³ Recumbent Length and Head Circumference at birth and discharge from NICU only⁴ AeroFact administered by nCPAP/nIMV or nCPAP/nIMV alone is to be initiated within 24 hours after birth. The anticipated duration of each AeroFact dosing is approximately approximately 2 hours.⁵ Re-dosing of AeroFact will be allowed if the RSS to maintain SpO₂ between 90 and 95% is 1.5 to 2.39 and at least two hrs. have elapsed since the start of the previous dose. If RSS is in range and FiO₂ >0.23, re-dosing will occur. If RSS is in range and FiO₂ is ≤0.23, re-dosing may occur at the discretion of the investigator. Up to 3 additional doses of AeroFact within 96 hrs. will be allowed.⁶ Oxygenation and respiratory parameters (FiO₂, SpO₂ [%], Positive-End Expiratory Pressure [PEEP]/CPAP [cm H₂O], Flow Rate [L/min], Mean Airway Pressure [Paw in cm H₂O], and Respiratory Support Status) will be obtained prior to dosing with AeroFact

delivery, every 15 minutes from the start of AeroFact dosing (T₀ to end of dose or a minimum of 2 hours). These parameters will be collected after the start of AeroFact administration or bolus instillation of surfactant for all groups.

⁷ Days 1-7 oxygen and resp. parameters will be obtained q 8 hrs., followed by daily from Days 8-28 and daily from 35 to 37 Wks. PMA and 39 through 40 Wks. PMA. Monitoring of O₂/resp parameters will occur at the same frequency for all groups.

⁸ Respiratory Support Status at 36 & 40 weeks PMA will be assessed by telephone if patient was discharged prior to that timepoint.

⁹ Nasal congestion/nasal aspiration will be assessed prior to and during each AeroFact dose or bolus instillation of surfactant for all groups.

¹⁰ Dosing tolerance completed at 4 and 24 hrs. after start of AeroFact administration or bolus instillation of surfactant for all groups.

¹¹ RAC will be performed if infant is on nasal cannula \leq 2 L/min and oxygen or nasal cannula $<$ 4 L/min in room air.

¹² Pulmonary outcomes will be assessed at 3, 6, 9 and 12 months corrected age and Neurologic Outcomes at 12 months corrected age. See Appendix II

TABLE OF CONTENTS

INVESTIGATOR'S SIGNATURE PAGE.....	3
1 CLINICAL PROTOCOL SYNOPSIS.....	4
TABLE OF CONTENTS	12

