Active drug will be reconstituted according to the AeroFact package insert instructions or the pharmacy/respiratory therapy manual. Active study drug doses distributed by the pharmacy or designee will be labelled with patient ID. Parameters required to set up the AeroFact delivery system to administer the proper study treatment regimen (patient weight and mg/kg) will be programmed into the controller by the unblinded member of the study staff. For active drug doses, an unblinded study member will set up the AeroFact delivery system. The AeroFact system will be primed and set to deliver the appropriate dose. If the infant is randomized to Control, the infant will continue to receive nCPAP/nIMV.

While preparing the set-up for the AeroFact system, a privacy screen will be placed around the delivery system to ensure the blind is maintained. Once the system is set up, the privacy screen will be moved aside to allow access to the infant and controller. Prior to aerosol administration, infant will be transitioned from their standard CPAP/nIMV to the AeroFact interface. Administration of AeroFact will be managed by the unblinded staff member. When adjustment of the AeroFact system is required (drug vial change, alarms, etc.), a privacy screen should be utilized to mask the treatment allocation.

Oxygenation, ventilation parameters, and nasal congestion/aspiration will be monitored every 15 minutes for the duration of dosing or a minimum of two hours after the start of dosing by a blinded study or staff member. Dosing tolerance will be evaluated at 4 and 24 hours after the start of each AeroFact dose. AeroFact aerosol delivery will be stopped at the time of dose completion, but AeroFact tubing/nebulizer and vial will remain in place for a minimum of 2 hours. The AeroFact delivery system will be removed from the patient's bedside after dosing is completed or 2 hours have elapsed (whichever is longer) and patient may be transitioned back to their standard nCPAP circuit. A new drug delivery circuit must be used for each subsequent dose administered.

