Infants receiving active drug will continue on nCPAP/nIMV after dose completion. If oxygenation and ventilation requirements increase within 96 hours after birth, AeroFact administration may be repeated up to three times for a total of 4 doses over the first 96 hours after birth. Re-dosing of AeroFact (same randomized group) will be allowed if the RSS to maintain SpO₂ between 90 and 95% is 1.5 to 2.39 and at least two hours have elapsed since the start of the previous dose:

- If FiO₂ > 0.23, re-dosing will occur.
- If FiO₂ ≤ 0.23, re-dosing is at the discretion of the investigator.

SpO₂ between 90-95% must be used to meet study eligibility through 96 hours for all study groups (Active/Control). Site-specific SpO₂ clinical guidelines may be used after 96 hours. Each site must use these guidelines uniformly across treatment groups. All infants randomized will be clinically managed until the criteria for treatment escalation have been met. If at any time the criteria for treatment escalation are met in any of the three treatment arms, intubation and/or bolus instillation of surfactant may be administered per site's standard of care. Oxygenation, ventilation parameters, nasal congestion/aspiration and dosing tolerance will be collected for each bolus instillation of surfactant.

Criteria for treatment escalation for AeroFact or nCPAP/nIMV only therapy includes any of the following:

1. Respiratory Symptom Severity (RSS) ≥ 2.4
2. Partial Pressure of Carbon Dioxide (PCO₂) > 65 mg Hg and/or pH < 7.20
3. Base deficit > 10 mEq/L, on two blood gases 4 hours apart
4. nCPAP > 8 cm
5. Three severe apneas with bradycardia within six hours requiring escalation of support
6. Infant's work of breathing has increased warranting escalating therapy, but infant does not meet RSS or other criteria above.

Data on all enrolled infants will be assessed through 40 weeks PMA or discharge from the NICU. Information to include: maternal/infant delivery, resuscitation history, oxygenation/ventilation parameters, concomitant medications of interest, and safety. Oxygenation and ventilation mode/parameters routinely monitored q 8 hours through Day 7, daily days 8 through 28, and daily at weeks 35 to 37 and 39 to 40 PMA/discharge. If an infant is discharged from the NICU prior to 36 and/or 40 weeks, a study member will call the family to verify the respiratory support status.

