6.6 Blinding

Clinical and research staff will remain blinded to dose level being administered with the exception of pharmacy staff or designee and respiratory therapy staff or designee. AeroFact drug delivery circuit will remain in line for the duration of dosing or a minimum of 2 hours, regardless of dose volume being administered.

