7 EFFICACY ENDPOINTS

7.1 Primary Efficacy Endpoint – Part I

- Proportion of infants requiring intubation/cannulation and bolus surfactant instillation in the first 7 days after birth

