10.1.3 Study Enrollment

10.1.3.1 Randomization

- Infant will be randomized to one of three study arms Active-Low Dose (108 mg/kg), Active High Dose-216 mg/kg or Control-nCPAP/nIMV alone. If twins or triplets are enrolled, only the first sibling will be randomized and subsequent siblings will receive the same treatment assignment.
- Randomization is a two-step process:
 - Step 1: a designated member of the study staff will obtain a randomization envelope for the appropriate gestational age group, which will randomize the infant to either the Active or Control group. The study staff will be made aware if the infant was randomized to the control group. The randomization envelope will be stored in a secure location within the infant's study file.
 - Step 2: active envelopes will be forwarded to the unblinded pharmacist or designee, where the active envelope will be opened and the Low or High dose group (108 mg/kg or 216 mg/kg) will be determined. Active drug dose will be calculated and dispensed according to the pharmacy manual instructions. Active drug will be administered according to study protocol.

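### Meeting an escalation criterion only permits the act that is the primary event, Active versus Control is open, and no protocol rule makes escalation practice uniform across arms within a site

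*Combined protocol and SAP*

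**What the plan says.** **Endpoint.** Section 7.1 defines the primary endpoint as "Proportion of infants requiring intubation/cannulation and bolus surfactant instillation in the first 7 days after birth". What is counted is a procedure that someone decides to perform.

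**Decision rule.** The synopsis says that once a criterion is met in any arm, "intubation and/or bolus instillation of surfactant may be administered at the discretion of the clinical team". Section 4.1 says instead that "intubation and/or bolus instillation of surfactant may be administered per site's standard of care". Both are permissive, and they name different reference points. One list of six criteria serves all three arms. Five are measured or counted. The sixth reads "Infant's work of breathing has increased warranting escalating therapy, but infant does not meet RSS or other criteria above".

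**Who knows the arm.** Section 10.1.3.1: "The study staff will be made aware if the infant was randomized to the control group". Section 4.1: "If the infant is randomized to Control, the infant will continue to receive nCPAP/nIMV"; no sham is described. Section 6.6: "Clinical and research staff will remain blinded to dose level being administered", apart from pharmacy and respiratory therapy staff. Section 12.6 likewise limits blinding to dose.

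**Uniformity rules.** After the sentence allowing site SpO₂ guidelines beyond 96 hours, Section 4.1 adds "Each site must use these guidelines uniformly across treatment groups". Section 6.7.1 asks for consistent vitamin A and corticosteroid use for BPD prophylaxis within a site. Neither rule covers escalation.

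**Data.** Section 10.1.5 sets one data-collection frequency for all arms, with oxygenation and ventilation parameters every 8 hours through Day 7. On blood gases the text is inconsistent. Section 8.1.5 includes clinically drawn gases that verify that escalation criteria were met. Table 1 footnote 2 refers to intubation, and Section 10.1.2 to intubation criteria.

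**The concern.** When the endpoint is a discretionary act and the decision-maker knows the arm, the event rate reflects both the infant's condition and the readiness to act. If a team waits longer in an Active infant because another aerosol dose is available, or escalates a control sooner on work of breathing, an apparent benefit is created or inflated. If a team holds back in controls, a real benefit is hidden.

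Both primary tests in Section 12.11 compare an Active dose with the same control arm, so one arm-aware habit would affect both. The result also feeds the choice of dose and dosing strategy for Phase 3 (Section 4.1).

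Stratifying and adjusting by site deals with differences in practice between sites. It does not deal with a difference between arms within a site.

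**Working it through.** **1. The plan's own figure.** Inputs from Section 12.3: 40% control, 20% Active, 80% power, alpha 0.05 (two-sided per Section 12.12), 5% dropout. With pooled variance under the null and p̄ = 0.30:

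n = [1.960 × √(2 × 0.30 × 0.70) + 0.842 × √(0.40 × 0.60 + 0.20 × 0.80)]² / 0.20² = 81.2, so 82 per arm.

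82 / 0.95 = 86.3, so 87 per arm and 3 × 87 = 261. The plan's numbers reproduce.

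**2. Illustration of unequal uptake.** Uptake is the share of infants meeting a criterion who then have the procedure. The documents give no uptake rate, so every uptake value here is an assumption. I read the plan's 40% as the rate of meeting a criterion. Then:

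primary event rate = proportion meeting a criterion × uptake.

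The test is the pooled two-proportion z test, 82 per arm, two-sided 0.05, by exact binomial enumeration. It covers one Active dose versus Control and ignores strata and sibling clustering.

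No drug effect, 40% meeting a criterion in both arms, control uptake 95% (control rate 0.40 × 0.95 = 0.38):

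| Active uptake | Active rate | Rejection |
|---|---|---|
| 95% | 0.38 | 4.8% |
| 90% | 0.36 | 5.6% |
| 85% | 0.34 | 8.1% |
| 80% | 0.32 | 12.5% |
| 70% | 0.28 | 27.5% |

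At 95% versus 80%, 12.2 of the 12.5 points favour Active. With the uptakes reversed, 12.2 favour Control. If 30% or 50% meet a criterion instead of 40%, the 95% versus 80% case gives 9.9% or 16.0%.

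**3. With a true effect (40% versus 20% meeting a criterion).**

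| Uptake, control / Active | Rates | Power |
|---|---|---|
| 95% / 95% | 0.38 v 0.19 | 77.7% |
| 80% / 95% | 0.32 v 0.19 | 48.2% |
| 95% / 80% | 0.38 v 0.16 | 89.8% |

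The 77.7% falls below the planned 80% only because 95% uptake is applied to the planning rates.

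**4. What a supportive analysis could recover.** Count an infant if a measured criterion was met or a bolus was given. Let capture be the share of met criteria that are recorded in infants given no bolus:

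supportive rate = met × [uptake + (1 − uptake) × capture].

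In the null case at 95% versus 80% uptake:

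| Capture | Rates | Rejection |
|---|---|---|
| 100% | 0.400 v 0.400 | 4.8% |
| 75% | 0.395 v 0.380 | 5.2% |
| 50% | 0.390 v 0.360 | 6.5% |
| 25% | 0.385 v 0.340 | 8.9% |

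The primary analysis rejects in 12.5% of trials in the same case.

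The work-of-breathing route stays open. Suppose 35% meet a measured criterion (uptake 95% v 80%) and 5% escalate on work of breathing only (uptake 95% v 50%). The primary rates are 0.38 and 0.35 × 0.80 + 0.05 × 0.50 = 0.305, and rejection is 17.1%. The supportive analysis gives 5.7% at full capture and 12.9% at 25% capture.

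**The case against.** The case on the other side has real weight.

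- **Existing safeguards.** One criteria list applies to all three arms. Section 4.1 ties action to the site's standard of care, which is a single reference for every arm. SpO₂ is held at 90–95% to 96 hours in all arms. Data-collection frequency is equal. Dose blinding protects the comparison between the two doses. All of this stands and narrows the concern. None of it requires a site to act alike in Active and Control infants.
- **Discretion is clinically necessary, and the trial is openly partially blind.** This stands. The point is not that discretion should go.
- **The illustration rests on assumed uptake.** This stands. A 5-point gap barely matters, and the larger figures need gaps of 15 to 25 points, for which the documents offer no evidence.
- **Other documents may already cover it.** The CRF and its completion guidelines, the Manual of Procedures and the SAP that Section 12 refers to were not available. This limits confidence.

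A reader might infer that the bias could never be examined afterwards. The documents do not support that: the 8-hourly values allow RSS ≥ 2.4 and nCPAP > 8 to be set against bolus use by arm. A reader might also infer that gases in infants not escalated go unrecorded. Section 8.1.5, read literally, includes a gas showing that a criterion was met, whether or not a bolus followed; the narrower wording elsewhere makes this an inconsistency. In the other direction, the first allocation paragraph of Section 4.1 might suggest that NICU staff are blind to Active versus Control. Its next paragraph and Sections 6.6, 10.1.3.1 and 12.6 limit the blind to dose.

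**Conclusion.** The concern holds as a gap in an open comparison with a discretionary endpoint. It does not show that bias will occur. Direction and size are unknown. Under the stated assumptions the effect runs from negligible (5.6% rejection at a 5-point uptake gap) to material (12.5% at 15 points), and it can favour either side.

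Part of it can be checked with data already planned. On the protocol text, four things cannot: which criterion triggered an escalation, which escalations rested on work of breathing alone, apnea counts in infants not escalated, and why a met criterion led to no bolus.

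A reader might expect the supportive analysis to settle the matter. It reduces the bias but does not remove it. It depends on capture and leaves the work-of-breathing route open. It also uses RSS and nCPAP, which depend on pressure settings chosen by staff who know the arm; the 4.8% at full capture assumes those settings do not differ by arm.

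This is a worthwhile, low-cost improvement, held with medium confidence because of the documents not seen.

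**What to change.** 1. **Wording.** Use one escalation sentence in the synopsis and Section 4.1, keep clinical discretion, and add: *Each site must apply its escalation practice, including use of the work-of-breathing criterion, in the same way in all treatment groups.*
2. **CRF.** Record the criterion that triggered each escalation. When a measured criterion is met and no bolus is given, record the time, the criterion (including clinically drawn gases and apnea episodes) and the reason. Align gas recording in Table 1 footnote 2 and Section 10.1.2 with Section 8.1.5.
3. **Tables by arm.** Report the proportion of infants meeting a measured criterion who had the procedure, and the proportion of primary events with no measured criterion met.
4. **Supportive analysis.** Analyse a measured criterion met while on non-invasive support, or a bolus, within 7 days. Take RSS and nCPAP from the 8-hourly values. Exclude the 15-minute dosing readings, which would give Active infants more chances to register a criterion. Gas and apnea criteria would come from the new CRF item, so also show the result with RSS and nCPAP only. State the three limits given in the verdict.

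The cost is one sentence in two places, a small CRF item, training at about 45 sites, one or two tables and one supportive analysis. The primary analysis, thresholds and treatment rules do not change.
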